14.2.2.6 Safety Analysis Set

Due to the challenges during the pandemic, the number of patients in a non-missing primary safety endpoint may drop below the lowest accepted power (80%) for approval trial design (< 78 patients). If the number of patients in the FAS is ≤ 78 , the safety analysis set will include the patients in the FAS and the last 18 sequentially enrolled patients from the FAS_RI. If the number of patients in the FAS is > 78 , then the safety analysis set will only include FAS patients.

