2.2 Sample Size

A minimum of 3 sites and up to 25 sites in the US are expected to participate in the study with approximately 100 pivotal subjects enrolled. No more than 15% of the pivotal subjects may be enrolled at a single investigational site.

The first 1-2 subjects enrolled by each investigator will be considered roll-in subjects to allow for physician experience with the investigational device. A maximum of 3 study investigators and 6 roll-in subjects will be permitted at each investigational site.

In total, up to 250 subjects will receive the investigational device as part of the clinical study.

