14.2.2 Analysis Populations

14.2.2.1 Full Analysis Set

The full analysis set (FAS) as defined by the ICH E9^v as "The set of subjects that is as close as possible to the ideal implied by the intention-to-treat principle." The guideline also defined the Intention-To-Treat Principle as the effect of a treatment policy can be best assessed by evaluating based on the intention to treat a subject (i.e., the planned treatment regimen) rather than the actual treatment given. Therefore, the FAS includes all patients that were consented, enrolled, and met the inclusion/exclusion criteria.

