14.2.5 Imputation for Endpoints

Due to the challenges related to the COVID-19 pandemic faced during the enrollment, some 30-day follow-up visits were outside of the protocol specified window. Therefore, for those patients whose 30-day visit was outside the window, the primary safety endpoint will be imputed based on the on visits that occurred at a minimum of 23 days post-discharge and is the closest to the 30-day visit. If there were no post-discharge visits, the primary safety endpoint will be imputed based on the site contacting the patient by phone as well as reviewing their records to determine the patient's primary safety endpoint status at 30 days. If even that information is not available, then the patient will be considered as missing the primary safety endpoint data.

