14.2.10.2.1 Sensitivity Analyses

There will be three sensitivity analyses:

1. The primary safety endpoint analysis will be repeated with the FAS patients only if FAS_RI patients are added to the safety analysis set
2. Tipping analysis based on missing data in the safety analysis set, as described in section 14.2.6.
3. The primary efficacy endpoint analysis will be repeated with the FAS_RI and the safety analysis set combined.

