### 3 Study Objectives

The study objective is to demonstrate the safety and efficacy of the investigational device to achieve hemostasis of common femoral artery access site in subjects undergoing percutaneous endovascular procedures utilizing 8-18Fr introducer sheath at the time that the enrollment was discontinued due to the COVID 19 pandemic.

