##### Design Tab

Solve For: Sample Size  
 Power Calculation Method: Binomial Enumeration  
 Max n for Binomial Enumeration: 10000  
 Higher Proportions Are: Better (H1: P > P0)  
 Test Type: Exact Test  
 N (Population Size): Infinite  
 Power: 0.80 to 0.85 by 0.01  
 Alpha: .05  
 Input Type: Differences  
 PB (Baseline Proportion): .94  
 d0 (Non-Inferiority Difference): -0.088  
 d1 (Actual Difference): 0

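### The safety roll-in rule is justified by evaluable patients but counts the whole FAS, and its cut-off of 78 does not hold power at 80%

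*Protocol*

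**What the plan says.** Protocol 14.2.2.6, repeated in SAP 7.2.6, gives a reason and then a rule. The reason is that, because of the pandemic, "the number of patients in a non-missing primary safety endpoint may drop below the lowest accepted power (80"%, with the danger zone given as fewer than 78 patients. The rule is that a FAS of 78 or fewer is supplemented with the last 18 sequentially enrolled FAS_RI patients; if the FAS is larger, "then the safety analysis set will only include FAS patients".

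Three other places matter:

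- **Who is in the FAS.** Protocol 14.2.2.1 says "the FAS includes all patients that were consented, enrolled, and met the inclusion/exclusion criteria". An observed endpoint is not required.
- **Who can be missing.** Protocol 14.2.5 uses out-of-window visits, then telephone contact and record review. If these yield nothing, "then the patient will be considered as missing the primary safety endpoint data".
- **Where 78 comes from.** The SAP 9.2 software run ("Power: 0.80 to 0.85 by 0.01") returned only two sample sizes, 78 and 86. Its definitions describe n as the evaluable sample size. The safety power tables (Protocol 14.1.2, SAP 6.2) list 78, 86 and 95.

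Planned enrolment is "approximately 100 pivotal subjects enrolled" (Protocol 2.2). SAP section 3 frames the objective "at the time that the enrollment was discontinued due to the COVID 19 pandemic".

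**The concern.** The rule decides who enters the primary safety analysis, and its stated purpose is to keep that test at 80% power or better. It falls short in three ways.

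1. **Wrong count.** The pandemic could reduce the numbers by stopping enrolment early or by losing 30-day status. A FAS count responds to the first and not to the second, although the stated reason is about non-missing endpoints. A number derived for evaluable patients is compared with a number that includes non-evaluable ones.
2. **Mismatched boundary.** The reason speaks of fewer than 78; the rule fires at 78 or fewer. At exactly 78 the sponsor's own power is 81.3%, yet 18 learning-curve patients are added.
3. **No floor at 78.** Nothing in the documents claims that every size above 78 gives 80% power, but the cut-off protects 80% only if that is true. Power of an exact binomial test is saw-toothed in n, so it has to be checked size by size.

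What is at stake is power, and clarity about the primary analysis set. The validity of the test is not in question.

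**Working it through.** **Inputs.** Performance goal p0 = 0.852, assumed true rate p1 = 0.94, one-sided alpha 0.05 (Protocol 14.1.2 and 14.1.2.1). The test requires the one-sided Clopper-Pearson lower 95% limit to exceed 85.2% (Protocol 14.2.10.2).

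**Formula.** For each evaluable n, let r be the smallest count with P(X ≥ r | n, 0.852) ≤ 0.05. Power is P(X ≥ r | n, 0.94). The Clopper-Pearson rule gives the same r at every n from 60 to 111.

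**Sponsor's rows reproduced.**

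| n | r | Type I error | Power | Plan |
|---|---|---|---|---|
| 78 | 72 | 0.0458 | 81.3% | 81.3% |
| 86 | 79 | 0.0486 | 85.6% | 85.6% |
| 95 | 87 | 0.0469 | 88.3% | 88.3% |

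**Between those rows.** From 78 to 85 the test allows six failures throughout, so each extra patient makes success harder until a seventh failure is allowed at 86.

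| n | r | Power |
|---|---|---|
| 79 | 73 | 80.5% |
| 80 | 74 | 79.6% |
| 81 | 75 | 78.7% |
| 82 | 76 | 77.9% |
| 83 | 77 | 77.0% |
| 84 | 78 | 76.1% |
| 85 | 79 | 75.2% |
| 86 | 79 | 85.6% |

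From 86 to 100, power is at least 80% except at 94 (r = 87, 79.7%). It is 82.8% at 90 and 85.4% at 100. The largest type I error for n from 60 to 110 is 0.0487.

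**Effect of counting the FAS.** The documents give neither a final FAS size nor a missing rate. Patients left missing are assumed to drop out of the denominator, which fits the SAP's evaluable n but is not stated in Protocol 14.2.10.2.

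- With the 10% dropout of SAP 9.2, a FAS of 79 leaves 79 × 0.9 = 71.1, about 71 evaluable; a FAS of 86 leaves 86 × 0.9 = 77.4, about 77. The rule adds no roll-ins. Power is 74.7% at 71 (r = 66) and falls to 68.4% at 77 (r = 72).
- The SAP's own inflation needs 78 / 0.9 = 86.7, so 87 enrolled, to leave 78 evaluable.
- Over the 22 FAS sizes from 79 to 100, power is below 80% at 7 with none missing, 10 with 4 missing and 13 with 8 missing. This is a grid over assumed values, not a probability.
- Missing data do not always lower power: a FAS of 85 with 7 missing leaves 78, and power rises from 75.2% to 81.3%.

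**Effect of adding 18 evaluable roll-ins.** Event-free total = Binomial(n, 0.94) + Binomial(18, q), tested with the r for n + 18. The value q = 0.90 is assumed, to represent a learning curve.

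| Evaluable FAS | Total | No roll-ins | q = 0.94 | q = 0.90 |
|---|---|---|---|---|
| 71 | 89 | 74.7% | 83.5% | 74.1% |
| 76 | 94 | 69.5% | 79.7% | 69.7% |
| 77 | 95 | 68.4% | 88.3% | 80.8% |
| 78 | 96 | 81.3% | 87.8% | 80.1% |

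**The case against.** The strongest reply is that the sponsor's figures are correct and the planned case is safe: 100 evaluable gives 85.4%, and 90 (10% dropout) gives 82.8%. That stands. But the rule is written for numbers below plan, and that is where it misfires.

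The saw-tooth belongs to every exact test, and software normally reports the smallest n that meets a target. That also stands, so a note beside the power table is enough; the table itself is not wrong. The boundary mismatch matters only at a FAS of exactly 78, where it has little effect.

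Lost follow-up is partly handled elsewhere, through the unscheduled visit and telephone contact (Protocol 7.5.4), the steps of 14.2.5, the reported missing counts (14.2.4) and the tipping-point analysis (14.2.6). These reduce or describe missingness. They do not decide who enters the primary safety set.

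Two practical points have force. In a single-arm study, the call or record review that makes a patient evaluable also reveals the outcome, so a count based on availability cannot be fully blind at the site. It can still be fixed centrally from a yes/no availability flag, and Protocol 14.2.4 already requires missing counts. Also, added roll-ins help only if they do about as well as pivotal patients: at 90% event-free, adding them to 71 to 76 evaluable gains almost nothing.

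Finally, enrolment has been discontinued, so no note can change the sample size, and without the final numbers nobody can say from the documents whether the gap will operate.

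**Conclusion.** The concern holds. The trigger and its stated reason count different patients, so the rule can add nobody when fewer than 78 are evaluable; at 71 to 77 evaluable, power is 74.7% falling to 68.4%. Separately, power is 79.6% falling to 75.2% at 80 to 85 evaluable, where no roll-ins are added even with complete data. These figures assume a true event-free rate of 94% and that patients missing the endpoint leave the denominator. The mismatch and the arithmetic are certain; the practical effect depends on a final FAS size and missing rate that the documents do not give. Type I error is unaffected. The sponsor should correct the rule, but it does not undermine the design at planned numbers.

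**What to change.** In Protocol 14.2.2.6 and SAP 7.2.6:

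- Make the trigger the number of FAS patients with a non-missing primary safety endpoint after all the steps of 14.2.5, and count the 18 roll-ins the same way.
- Fix that count from endpoint availability alone, before safety outcomes are reviewed.
- Reconcile fewer than 78 with 78 or fewer.
- State beside the safety power table that 80 to 85 evaluable patients give 75% to 80% power.

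Protocol 14.2.2.5 and SAP 7.2.5 are built the same way for efficacy (a reason based on non-missing endpoints, a PPS count, fewer than 86 against 86 or fewer), so the wording should be aligned there too.

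Raising the safety cut to fewer than 86 is optional. It brings in learning-curve patients more often and still does not guarantee 80%: 76 + 18 = 94 gives 79.7%, and 62 to 67 plus 18 makes 80 to 85, back in the dip.

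The cost is a sentence in each safety section, a note at the table, and the matching efficacy edit. The drawback is that roll-ins may enter the primary safety set more often. The planned sensitivity analysis already shows the result without them: "The primary safety endpoint analysis will be repeated with the FAS patients only" when roll-ins have been added. The tipping-point analysis and the reporting of missing counts stay as they are.

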14.2.3 Poolability Analyses

All investigational sites will follow the requirements of a common protocol and standardized data collection procedures and forms. The primary endpoints will be presented separately (major and minor complications will be presented separately for the primary safety endpoint) for each site using descriptive statistics. Poolability of the primary endpoints across the investigational site will be evaluated using a regression model with fixed effects for the site using the FAS for the primary safety endpoint and PPS for primary efficacy endpoint. Sites enrolling less than five subjects will be combined with the geographically nearest site. If the p-value for the site effect is <0.15 , additional exploratory analyses will be performed to understand any variations in outcomes by site.

14.2.4 Handling of Missing Data

All attempts will be made to limit the amount of missing data. For all analyses of the primary endpoints, the number of observations available, patients with no primary safety endpoint information, and patients with imputed results will be reported so the reader can assess the impact of missing data.

14.2.5 Imputation for Endpoints

Due to the challenges related to the COVID-19 pandemic faced during the enrollment, some 30-day follow-up visits were outside of the protocol specified window. Therefore, for those patients whose 30-day visit was outside the window, the primary safety endpoint will be imputed based on the on visits that occurred at a minimum of 23 days post-discharge and is the closest to the 30-day visit. If there were no post-discharge visits, the primary safety endpoint will be imputed based on the site contacting the patient by phone as well as reviewing their records to determine the patient's primary safety endpoint status at 30 days. If even that information is not available, then the patient will be considered as missing the primary safety endpoint data.

14.2.6 Sensitivity Analyses

Sensitivity analyses will be performed to assess the impact of missing data for the primary safety endpoint; a tipping point analysis will be conducted in which subjects censored without a 30 days follow-up visit are sequentially imputed as failures at the time of censoring. The primary safety endpoint analysis will be repeated after each sequentially imputed failure.

Sensitivity analyses will be performed to assess the impact of missing data for the primary efficacy endpoint; a tipping point analysis will be conducted in which subjects without a TTH are sequentially imputed as 15 minutes (the performance goal). The primary efficacy endpoint analysis will be repeated after each sequentially imputed value.

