14.1.1 Primary Efficacy Endpoint

The primary effectiveness hypothesis will be tested by comparing the primary effectiveness endpoint, mean time-to-hemostasis (TTH), against a performance goal (PG) of 15 minutes.

The comparison to the performance goal will be based on the following statistical hypothesis test:

$$H_0: \mu_{TTH} \geq 15$$

$$H_A: \mu_{TTH} < 15$$

where μ_{TTH} is the mean time-to-hemostasis in minutes.

The test will be based on whether the upper one-sided 97.5% confidence limit (based on a t-distribution)^{iv} is less than 15. Assuming similar performance to Perclose ProGlide®, with a mean time-to-hemostasis of 9.8 minutes and a standard deviation of 17 minutes the sample sizes for power levels from 80 to 90%

a Table 3: Primary Efficacy Endpoint Sample Sizes for Various levels of Power

Power	Sample Size	Maximum Observed Time (minutes) and still reject H_0
80.0%	86	10.8
81.4%	89	10.9
82.3%	91	10.9
83.1%	93	10.9
84.3%	96	11.0
85.0%	98	11.1

Successful rejection of the null hypothesis will mean that the PG has been met.

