14.2.2.5 Efficacy Analysis Set

Due to the challenges during the pandemic, the number of patients in a non-missing primary efficacy endpoint may drop below the lowest accepted power (80%) for approval trial design (< 86 patients). If the number of patients in the PPS is ≤ 86 , the efficacy analysis set will include the patients in the PPS and the last 18 sequentially enrolled patients from the PPS_RI. If the number of patients in the PPS is > 86 , then the efficacy analysis set will only include PPS patients.

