14.2.10 Analysis of Study Endpoints

Study success is defined as the successful rejection of the corresponding null hypotheses for each of the primary safety and effectiveness endpoints.

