14.2.10.1.1 Sensitivity Analyses

There will be three sensitivity analyses:

1. The primary efficacy endpoint analysis will be repeated with the PPS patients only if PPS_RI patients are added to the efficacy analysis set
2. Tipping analysis based on missing data in the efficacy analysis set as described in section 14.2.6
3. The primary efficacy endpoint analysis will be repeated with the PPS_RI and the efficacy analysis set combined.

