### 7.4.2 Sensitivity Analyses

Sensitivity analyses will be performed to assess the impact of missing data for the primary safety endpoint; a tipping point analysis will be conducted in which subjects censored without a 30 days follow-up visit are sequentially imputed as failures at the time of censoring. The primary safety endpoint analysis will be repeated after each sequentially imputed failure.

Sensitivity analyses will be performed to assess the impact of missing data for the primary efficacy endpoint; a tipping point analysis will be conducted in which subjects without a TTH are sequentially imputed as 15 minutes (the performance goal). The

Statistical Analysis Plan		Page 21 of 31
Sponsor Terumo Medical Corporation	Study Cross-Seal IDE Trial: Prospective, Multi-Center, Single Arm Study of the Cross-Seal Suture-Mediated Vascular Closure Device System	Version 1.4

primary efficacy endpoint analysis will be repeated after each sequentially imputed value.

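### The efficacy tipping-point analysis imputes missing TTH at 15 minutes, the null value itself, so it is practically unable to tip

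*Protocol*

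**What the plan says.** Protocol 14.1.1 tests mean TTH "against a performance goal (PG) of 15 minutes", with H0 that the mean is at least 15. The decision rule is stated as follows: "The test will be based on whether the upper one-sided 97.5% confidence limit (based on a t-distribution") is less than 15.

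For missing TTH, Protocol 14.2.6 plans that "a tipping point analysis will be conducted in which subjects without a TTH are sequentially imputed as 15 minutes (the performance goal"), with the primary analysis repeated after each imputation. SAP 7.4.2 has the same rule: "subjects without a TTH are sequentially imputed as 15 minutes (the performance goal"). Neither document plans any other imputed value.

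Protocol 14.2.10.1.1 lists three efficacy sensitivity analyses. One is "Tipping analysis based on missing data in the efficacy analysis set as described in section 14.2.6". The other two only vary which roll-in subjects are included (the SAP has the same list under 7.7.1).

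For the primary safety endpoint, 14.2.6 uses a different kind of rule: subjects without 30-day follow-up "are sequentially imputed as failures at the time of censoring".

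**The concern.** A tipping-point analysis asks how bad the missing outcomes would have to be before the conclusion reverses. It is informative only if the imputed values can become unfavourable enough to reverse it. The safety rule does this, because a failure is the unfavourable outcome. The efficacy rule stops at the null value, so missing values worse than the performance goal are never examined. Yet an SD of 17 around a mean of 9.8 implies that some TTH values exceed 15.

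This is the only planned look at missing primary efficacy data. Protocol 14.2.2.5 allows that "the number of patients in a non-missing primary efficacy endpoint may drop below the lowest accepted power (80"%), which it puts at fewer than 86 patients. If nearly every passing trial would show no tipping point under the stated rule, that result would be read as robustness without having tested it.

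**Working it through.** **Inputs.** Null value 15, assumed mean 9.8, SD 17, one-sided alpha 0.025 and n = 86 (Protocol 14.1.1; SAP 9.1). The documents give no expected number of missing TTH. As an illustration I use k = 10, which is the SAP 9.1 dropout table's own figure (10% dropout, 86 evaluable, 96 enrolled).

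**The plan's own figure.** Noncentral-t power with 85 degrees of freedom and noncentrality (15 − 9.8)/17 × √86 = 2.837 is 0.80080, as printed in SAP 9.1. The other five rows also reproduce.

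**Why 15 does not tip.** Let n values with mean m and SD s be observed, and add k values equal to 15, so N = n + k. Two sums are unchanged by the imputation:

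- S = n(15 − m) = 86 × 5.2 = 447.2
- Q = (n − 1)s² + n(15 − m)² = 85 × 289 + 86 × 27.04 = 26,890.44

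The test statistic is t = S × √((N − 1)/N) / √(Q − S²/N).

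- k = 0: 447.2 × √(85/86) / √24,565 = 2.837
- k = 10: 447.2 × √(95/96) / √24,807.2 = 2.824
- k unlimited: 447.2 / √26,890.44 = 2.727, which equals t₀ × √(n/(n − 1 + t₀²)) with t₀ = 2.837

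Meanwhile the critical value falls from 1.988 to about 1.96.

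| Imputed at 15 min | Mean | SD | t | Upper 97.5% limit |
|---|---|---|---|---|
| 0 | 9.80 | 17.00 | 2.837 | 13.44 |
| 10 | 10.34 | 16.16 | 2.824 | 13.62 |
| 86 | 12.40 | 12.27 | 2.780 | 14.25 |
| 1,000 | 14.59 | 4.96 | 2.735 | 14.88 |

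The limit approaches 15 but does not reach it.

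**Which passing results could reverse.** With SD 17 the trial passes if the observed mean is below 15 − 1.9883 × 17/√86 = 11.355. With 10 imputed, a pass reverses only if the mean is above about 11.354; with unlimited imputation, only if it is above about 11.345. (The tables in Protocol 14.1.1 and SAP 6.1 print 10.8 as the largest passing mean at n = 86, which this formula does not give. Starting from 10.8, the 15-minute rule still never tips.)

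In 1,000,000 simulated trials under normality at the design values, 80.2% pass. Of these, 0.019% reverse with 10 imputed at 15 and 0.18% with a million imputed. A lognormal with the same mean and SD gives about 0.01% with up to 10 imputed.

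**The same calculation above 15.** For an imputed value v:

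- mean′ = (nm + kv)/(n + k)
- var′ = [(n − 1)s² + nk/(n + k) × (v − m)²]/(n + k − 1)
- upper limit = mean′ + t(0.975, n + k − 1) × √(var′/(n + k))

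Example, v = 30 and k = 8: mean′ = (842.8 + 240)/94 = 11.52, var′ = 27,551.5/93 = 296.25, and upper limit = 11.52 + 1.986 × √(296.25/94) = 15.04.

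| Imputed value (min) | First k that tips | Limit just before, then at, that k |
|---|---|---|
| 20 | 25 | 14.97, 15.02 |
| 30 | 8 | 14.86, 15.04 |
| 45 | 4 | 14.75, 15.16 |
| 60 | 3 | 14.84, 15.50 |

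Read the other way, with 1, 2, 5 or 10 missing, each value would have to be 100.6, 64.4, 37.4 or 26.8 minutes to tip the result.

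**Safety rule for contrast.** At 81 of 86 event-free (an illustrative result), the one-sided 95% Clopper-Pearson lower limit is 88.2%. Adding failures gives 86.8% (81/87), 85.6% (81/88) and 84.4% (81/89). The third failure takes it below the 85.2% goal, so that rule can tip.

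**The case against.** The algebra is hard to dispute, so the best case against acting concerns weight.

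- **Few values may be missing.** TTH is recorded at the index procedure (Protocol 7.2), so loss to follow-up does not remove it. The efficacy analysis set is built on the per-protocol set, which already excludes subjects with adjunctive therapy beyond light compression (Protocol 14.2.2.2). The 10% dropout figure was not designed for this. The share of passing trials that reverse depends strongly on k: under normality, imputing 30 or 60 minutes reverses 4% or 15% with one missing, 8% or 33% with two, and 50% or 99.8% with ten.
- **Normality exaggerates some contrasts.** A normal with mean 9.8 and SD 17 puts 28% of times below zero. Under a lognormal, the 50% at 30 minutes and k = 10 becomes 29%.
- **Fifteen minutes is not lenient for this device.** The longest TTH in the two earlier studies were 13:00 and 11:54 (Protocol 1.5.1, 1.5.2).
- **The analysis is supportive.** "Study success is defined as the successful rejection of the corresponding null hypotheses for each of the primary safety and effectiveness endpoints". Protocol 14.2.4 also requires the numbers available and imputed to be reported.

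These points stand and limit the importance of the concern. They bear on the size of the illustrative contrasts, not on the near-zero chance of tipping at 15, which holds under both distributions. If few values are missing, an informative analysis would show so: one missing value would need to exceed 100 minutes to matter at the design values. The present rule cannot provide that evidence.

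**Conclusion.** The concern holds. At n = 86 and SD 17, the rule can overturn a pass only when the observed mean lies within about 0.001 minute of the 11.355 cut-off with 10 missing, or about 0.01 minute with any number missing. Its outcome is nearly fixed in advance.

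This does not depend on the 9.8 and 17 assumption: a larger margin below 15 leaves the rule even further from tipping. If TTH resembled the CE study (mean 1.19 minutes; SD not reported, assumed 2.5 to 5), then 30, 45 or 60 minutes would tip only at 57, 27 or 17 subjects, so a better analysis might well show real robustness.

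The primary test and the success criterion are unaffected. The practical importance depends on how many TTH values are missing, which the documents do not say. It is worth correcting because the planned analysis would otherwise support a claim that it has not tested.

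**What to change.** In Protocol 14.2.6 and SAP 7.4.2, replace the single 15-minute value with a pre-specified increasing range of values above 15 minutes, applied sequentially to subjects in the efficacy analysis set without a TTH. Report the smallest value and number of subjects at which the upper 97.5% limit reaches 15. The 20, 30, 45 and 60 minutes used above are illustrative, since the documents give no source for a grid; the sponsor should choose and justify one. The maximum observed TTH is a useful grid point only if it exceeds 15.

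The cost is one sentence in each document and a few extra runs. The only downside is that a tipping point may appear.
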